11.4 Year 2 Data Analysis

When the 12-month follow-up is complete for the primary analysis, the database will be locked. Post-12 month information will remain fully masked until completion of 24-month follow-up.

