The objectives of this study are to evaluate the safety and efficacy of Zimura intravitreal administration in patients with geographic atrophy secondary to age-related macular degeneration (AMD).

Primary Efficacy Outcome

The primary efficacy outcome is the mean rate of growth (slope) estimated based on GA area measured by FAF in at least 3 time points: Baseline, Month 6, and Month 12 (square root transformation).

[REDACTED]

[REDACTED]

- [REDACTED]
- [REDACTED]

[REDACTED]

[REDACTED]

- [REDACTED]
- [REDACTED]
- [REDACTED]
- [REDACTED]

CONFIDENTIAL

- [REDACTED]
- [REDACTED]
- [REDACTED]
- [REDACTED]
- [REDACTED]
- [REDACTED]
- [REDACTED]
- [REDACTED]
- [REDACTED]

[REDACTED]

[REDACTED]

[REDACTED]

- [REDACTED]
- [REDACTED]

Safety Outcomes

The following safety outcomes will be evaluated:

- Adverse events (AEs)
- Serious adverse events (SAEs)
- Vital signs (pulse, systolic and diastolic blood pressure)
- Ophthalmic variables (ophthalmic examination, best corrected visual acuity (BCVA), low luminance BCVA (LLBCVA), intraocular pressure (IOP))
- Electrocardiography (ECG) (12-lead)
- Laboratory variables (blood: hematology, renal function, hepatic function, and electrolytes; urinalysis)

STUDY DESIGN AND SAMPLE SIZE

Approximately 400 patients will be randomized at Day 1 in a 1:1 ratio to the following monthly treatment groups:

- Zimura 2 mg
- Sham

Patients receiving monthly Zimura 2 mg will be re-randomized at Month 12 in a 1:1 ratio to the following treatment groups:

CONFIDENTIAL

- Zimura 2 mg administered monthly from Month 12 – Month 23
- Sham administered at Months 12, 14, 16, 18, 20, and 22, and Zimura 2mg administered every other month at Months 13, 15, 17, 19, 21, and 23

All patients who were initially randomized to Sham (at Day 1) will continue with monthly Sham injections through Month 23.

All patients will have a final follow-up visit at Month 24.

The trial consists of a total treatment period of 24 months. This SAP covers all analyses to be performed on 1 year (12 months) data.

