Only first year AE data will be included in the following analyses. Treatment Emergent Adverse Events (TEAEs) from the first year will be defined as starting after the first dose of study drug until prior to Month 12 injection. If a Month 12 injection does not exist, the end of the first year is defined as the Month 12 visit (or target of 365.25 days after the first dose if no Month 12 visit) or 30 days after the last injection, whichever is later.

All AEs will be coded using MedDRA™ (version 23.0 update) terms.

- An overview of TEAEs will be provided. A second overview of TEAEs will be provided which displays the overall summary of TEAEs by the categories ‘Study Eye’, ‘Non-Study Eye’, and ‘Non-Ocular’. In addition, the number and percentage of patients with TEAEs will be tabulated for each treatment group and in total by system organ class (SOC) and preferred term (PT). The number and percentage of the subjects who experienced at least one TEAE will be included. Subjects will only be counted once for each preferred term. In case that a subject experienced the same event more than once, the worst severity will be presented.
- Tabular summaries of the following AEs will be provided by SOC and PT:
 - Summary of TEAEs
 - All TEAEs regardless of the relationship to study treatment
 - All TEAEs regardless of the relationship to study treatment with frequency of $\geq 5\%$ in any treatment arm.

CONFIDENTIAL

-
- TEAEs related to study treatment
 - TEAEs related to injection procedure
 - TEAEs by the maximum severity grade
 - TEAEs related to study treatment by the maximum severity grade
 - TEAEs related to injection procedure by the maximum severity grade
 - All Ocular TEAEs by study eye and fellow eye
 - Treatment related Ocular TEAEs by study eye and fellow eye
 - Injection procedure related Ocular TEAEs by study eye and fellow eye
 - Ocular TEAEs (study eye) by the maximum severity grade
 - Treatment related Ocular TEAEs (study eye) by the maximum severity grade
 - Injection procedure related Ocular TEAEs (study eye) by the maximum severity grade
 - TEAEs with high level term of cataract conditions by study eye and fellow eye
 - TEAEs leading to discontinuation of study drug
 - Treatment related TEAEs leading to discontinuation of study drug
 - Injection procedure related TEAEs leading to discontinuation of study drug
 - Ocular TEAEs (study eye) leading to discontinuation of study drug
 - TEAEs leading to death
 - Treatment related TEAEs leading to death

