Descriptive statistics at each time point up through and including the Month 12 visit will be used to display the changes from Baseline for pulse and blood pressure (systolic and diastolic). Mean change of pulse and blood pressure (systolic and diastolic) from Baseline to the last measurement will be provided.

OPHTHALMIC VARIABLES

Ophthalmic Examination. The following ophthalmic examination variables will be analysed by shift table from Baseline to the pre-injection examination on Month 12 or last visit available whichever comes later (normal/abnormal, unless otherwise specified below):

- Examination of the motility
- Inspection of the lids/lacrimal/lashes
- Examination of the conjunctiva/sclera
- Inspection of the cornea

CONFIDENTIAL

-
- Examination of the iris
 - Examination of the pupils
 - Inspection of the lens status (aphakic, pseudo-phakic, phakic; if phakic, nuclear/PSC/cortical 0, 1, 2, 3, 4), including a listing of subjects with a change in lens status for study eye and (separately) for fellow eye
 - Examination for posterior vitreous detachment
 - Inspection of the optic nerve
 - Inspection of the macula
 - Examination of the retinal vessels

The following ophthalmic examination variables will be analysed by shift table from Baseline through Month 12 or last visit available whichever comes later, on a monthly basis (normal/abnormal, unless otherwise specified below), and from pre-injection to post-injection at each monthly injection

- Examination of anterior chamber activity: Cells (0, trace, 1+, 2+, 3+, 4+)
- Inspection for vitreous haze (0, 1+, 2+, 3+, 4+)
- Examination for vitreous haemorrhage
- Examination of the peripheral retina

Intraocular Pressure. IOP will be summarized by visit, including all pre-injection, “IOP after first injection”, and “IOP after second injection” measurements for applicable visits. An additional tabular summary of the percentage of subjects in categories of IOP will be presented by treatment group, visit, and injection time (pre-injection, IOP after first injection, IOP after second injection).

“IOP after injection” is defined as the IOP measurement that is closest in time to the protocol-specified post-injection timepoint (but at least 30 minutes post-injection). If there are two closest measurements equidistant to this timepoint, then the measurement after the protocol-specified timepoint will be used.

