Mean IOP over time of all scheduled measurements (pre-injection, IOP after first injection, and IOP after second injection) will be plotted.

CLINICAL LABORATORY DETERMINATION

- All laboratory data will be listed and values falling outside normal ranges will be identified, whether they will be deemed clinically relevant or not.
- Laboratory data will also be summarized in tables presenting values at each scheduled visit up through the Month 12 visit
- Value changes from Baseline to each scheduled visit up through the Month 12 visit

CONFIDENTIAL

-
- A summary table of all analytes with the Baseline mean and the mean change from Baseline to the last value observed
 - A summary table of all analytes with the Baseline median and the median change from Baseline to the last value observed

For the following parameters:

- Hematological parameters (hemoglobin, white blood cells, platelets, neutrophils (absolute numbers), lymphocytes (absolute numbers), monocytes (absolute numbers), eosinophils (absolute numbers), basophils (absolute numbers)),
- Renal function parameters (serum creatinine and BUN),
- Hepatic function parameters (serum bilirubin, alkaline phosphatase, GGT, SGOT/AST, and SGPT/ALT),
- Electrolytes (sodium, potassium, chloride, carbon dioxide, calcium, and phosphate),
- Complete urinalysis parameters (complete urinalysis including specific gravity, protein, blood, etc.),
- Serum pregnancy test (if of child-bearing potential).

Additional urine or serum pregnancy testing may be performed during the course of the study at the discretion of the investigator, or in accordance with local requirements or regulations.

The incidence of subjects with “Notable Laboratory Values” after the first dose of study drug will be evaluated using the criteria for Notable Laboratory Values given below. Only data collected after the first dose of study drug, up to the laboratory data taken at the Month visit (before Month 12 treatment is administered) will be included; if there is no Month 12 visit, data will be included up to a target of 365.25 days after date of first dose, or 30 days after the last dose of study drug, whichever is later.

By-subject listings of all notable laboratory values will also be provided; for each subject who has an analyte with a notable value, all values of that particular analyte taken during the study will be presented in the listing, and the notable value, and any values outside of normal limits, will be identified.

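### Year 1 SAP: the ophthalmic shift tables and last-value safety summaries have no Month 12 limit, which conflicts with the SAP's 12-month scope and with Protocol 11.4

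*SAP*

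**What the plan says.** The Year 1 SAP sets its scope under Study Design and Sample Size: "This SAP covers all analyses to be performed on 1 year (12 months) data". Its Introduction leaves any 18- and 24-month analysis to a separate SAP. The design section also states that "Patients receiving monthly Zimura 2 mg will be re-randomized at Month 12 in a 1:1 ratio", to monthly or every-other-month dosing. The every-other-month group receives Sham at the even-numbered months from 12 to 22. Protocol 11.4 locks the database once 12-month follow-up is complete and adds: "Post-12 month information will remain fully masked until completion of 24-month follow-up".

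Within the Safety Evaluation of the Year 1 SAP, cut-offs are written in three ways.

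- **Open-ended.** Under Ophthalmic Variables, eleven examination items are analysed by "shift table from Baseline to the pre-injection examination on Month 12 or last visit available whichever comes later". Four more (anterior chamber cells, vitreous haze, vitreous haemorrhage, peripheral retina) are analysed by "shift table from Baseline through Month 12 or last visit available whichever comes later, on a monthly basis", with pre- to post-injection shifts at each injection.
- **Silent.** Vital Signs, Clinical Laboratory Determination and ECG each include a comparison of Baseline with the final recorded value. Those sentences give no date limit.
- **Capped, with a fallback.** Under Adverse Events, "Only first year AE data will be included in the following analyses", and TEAEs stop before the Month 12 injection. If there was no Month 12 injection, the first year ends at the Month 12 visit (or day 365.25) "or 30 days after the last injection, whichever is later". Notable laboratory values stop at the Month 12 sample taken before treatment. If there was no Month 12 visit, they run to day 365.25 "or 30 days after the last dose of study drug, whichever is later". By-visit vital-sign and laboratory tables stop at Month 12.

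**The concern.** The Year 1 safety tables are meant to compare 12 months of monthly Zimura 2 mg with Sham. An end point set at the later of Month 12 and the last visit does not do that for a patient who already has Year 2 visits.

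Three things are at stake. The Zimura column would mix monthly dosing with the every-other-month schedule. Length of follow-up would depend on when a patient enrolled. And post-Month-12 findings would be tabulated by arm while the protocol says they stay masked.

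**Working it through.** No figure in the plan needs reproducing here. The check sets the rules side by side and adds date arithmetic for the fallbacks.

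**1. Which patients have a later visit at the lock?** Ophthalmic examination is scheduled at every monthly visit to Month 24 (Protocol Section 3). The lock waits until 12-month follow-up is complete (Protocol 11.4), so patients enrolled earlier have passed Month 12 by then. For each one who stayed in the study and has a later visit recorded, the later of Month 12 and the last visit is a Year 2 visit.

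**2. Does the 12-month scope settle it?** If the data stopped at Month 12, the last visit could never be later than Month 12, and the choice of the later one would do no work. Neighbouring sections state a Month 12 limit outright, so a programmer could read its absence here as deliberate. The scope statement and the table rule point in opposite directions.

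**3. What do the later visits contain?** About 400 patients randomised 1:1 gives about 200 on Zimura. Re-randomising them 1:1 gives at most 200 / 2 = 100 on every-other-month dosing. If 10% to 20% leave before Month 12 (an assumption), the figure is 180 / 2 = 90 to 160 / 2 = 80, or 45% to 40% of the original arm. The Safety Population keeps anyone who ever received Zimura in the Zimura group. Sham visits of the every-other-month patients would therefore count as Zimura visits in the monthly and pre- to post-injection tables.

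**4. How far do the fallbacks reach?** Take a month as 30.4375 days. The window ends at the later of day 365.25 and the last injection day + 30.

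| Last injection | Injection day + 30 | Excess over day 365.25 |
|---|---|---|
| Month 11 | 334.8 + 30 = 364.8 | none |
| Month 13, Month 12 missed | 395.7 + 30 = 425.7 | about 60 days |
| Month 18, Month 12 missed | 547.9 + 30 = 577.9 | about 213 days |
| Month 23, Month 12 missed | 700.1 + 30 = 730.1 | about 365 days |

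A Month 11 injection given 7 days late, the edge of its visit window, ends at 341.8 + 30 = 371.8, an excess of under 7 days. A material excess needs a patient who misses Month 12 and then resumes. A scheduled Month 18 laboratory sample (day 547.9) enters only if the whole Month 12 visit was missed and a dose was given on or after about day 547.9 - 30 = 517.9, roughly Month 17.

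**5. How many patients?** This cannot be derived. The documents give neither the Year 1 lock date nor the number who miss Month 12 and resume. The only dates available are 16 November 2020, by which the 38 patients with the stratification error had been randomised (Year 1 SAP, Sensitivity Analysis for Stratification Error), and 3 August 2022, when Year 1 was still masked (Year 2 SAP, Introduction). They are 625 days apart, and 625 / 30.4375 = 20.5 months. Visits to about Month 20 are therefore possible for the earliest patients, but this is calendar time and does not show what the locked data contain.

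**The case against.** The strongest reply is that the documents, read together, already exclude Year 2 data. The SAP is limited to 12 months, later analyses go to another SAP, and the protocol keeps later information masked. On that reading, the last visit means the last visit within the Year 1 data. The Year 2 SAP (4.3.5) uses the same sentence with Month 24, where it does little harm because Month 24 is the final visit. That suggests template wording. The details of the visit windows are in an appendix that cannot be read in the public copy.

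Much of this stands. The capped reading is probably what was intended, and a reader who inferred that the Year 1 tables are bound to include Year 2 data would go too far. But the reply shows a contradiction that could be programmed either way. It does not show a rule that gives the right cut. The visible visit-window text only lets an unscheduled or early-withdrawal visit replace a missing scheduled one, so it does not limit these tables.

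A reader might also infer that Year 1 safety rules in general lack a Month 12 cap. The documents do not support that. The main TEAE rule, the main notable-laboratory rule and the by-visit vital-sign and laboratory tables are all capped. The two fallbacks also have a sensible purpose: 30 days of follow-up after the last dose for patients who stop treatment, in line with the adverse event collection period.

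**Conclusion.** The point holds for the two ophthalmic shift-table rules, which, followed literally, give the wrong data cut for every patient with a visit after Month 12 at the Year 1 lock. It holds more weakly for the last-value summaries of vital signs, laboratory results and ECGs, which state no limit and depend on the general scope statement. The TEAE and notable-laboratory fallbacks are materially open-ended only for patients who miss the Month 12 injection or visit and later resume. The excess could then be about 60 to 365 days for a patient whose last injection is between Month 13 and Month 23.

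Severity is minor to moderate. These are descriptive safety tables, and primary efficacy is not affected. The conclusion assumes that post-Month-12 visits are present in the data from which the Year 1 tables are made; the documents do not say how that extract is cut. No count of affected patients should be quoted.

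**What to change.** In the Year 1 SAP:

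- **Shift tables:** define the end point as the Month 12 pre-injection examination or, if there is none, the last examination before it. End the monthly tables at the same point. Pre- to post-injection shifts should then stop at the last Year 1 injection, because the Month 12 injection follows re-randomisation (Protocol 10.2.3.25).
- **Last-value summaries** (vital signs, laboratory, ECG): limit them to data up to and including the pre-injection Month 12 visit.
- **The two fallbacks:** count only injections given before the Month 12 visit (or day 365.25 if there was none), and never let the window run past the first Year 2 injection.

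The cost is a few words and one date cut-off in the programs, with no new data. The Year 2 SAP says that the Year 1 analysis has been done, so the practical step is to check which cut the programs applied, record it, and re-run the affected tables if they used later visits.

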2 SUMMARY OF PROTOCOL ISEE2008

SYNOPSIS	
TITLE:	A Phase 3 Multicenter, Randomized, Double Masked, Sham-Controlled Clinical Trial to Assess the Safety and Efficacy of Intravitreal Administration of Zimura (Complement C5 Inhibitor) in Patients with Geographic Atrophy Secondary to Age-Related Macular Degeneration
OBJECTIVES:	The objectives of this study are to evaluate the safety and efficacy of Zimura intravitreal administration in patients with geographic atrophy secondary to age-related macular degeneration (AMD)
TRIAL DESIGN:	
Approximately 400 patients will be randomized at Day 1 in a 1:1 ratio to the following monthly treatment groups:
 
 • Zimura 2 mg • Sham 
Patients receiving monthly Zimura 2 mg will be re-randomized at Month 12 in a 1:1 ratio to the following treatment groups:
 
 • Zimura 2 mg administered monthly from Month 12 through Month 23 • Sham administered at Months 12, 14, 16, 18, 20, and 22, and Zimura 2 mg administered every other month at Months 13, 15, 17, 19, 21, and 23 
All patients who were initially randomized to Sham (at Day 1) will continue with monthly Sham injections through Month 23
 
All patients will have a final follow up visit at Month 24

ENDPOINTS:	
Primary Efficacy Endpoint:
 
 • The mean rate of growth (slope) estimated based on GA area measured by FAF in at least 3 time points: Baseline, Month 6, and Month 12 (square root transformation) 
Safety Endpoints:
 
 • Adverse events (AEs) • Vital signs (pulse, systolic and diastolic blood pressure) • Ophthalmic findings (best corrected visual acuity [BCVA], low luminance BCVA, intraocular pressure [IOP], and ophthalmic examination) • Electrocardiogram (ECG) (12-lead) • Laboratory variables (blood: hematology, renal function, hepatic function and electrolytes; urinalysis)

PLANNED SAMPLE SIZE:	Approximately 400 patients will be enrolled
SUBJECT SELECTION:	Patients of either gender aged 50 years or greater diagnosed with geographic atrophy secondary to AMD
FORMULATION:	
INVESTIGATIONAL DRUG DOSAGE:	Patients will receive a minimum of 18 doses and a maximum of 24 doses of Zimura at a dose of 2 mg

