AMD, at its early stages, presents with drusen and abnormalities of retinal pigment epithelium (RPE). As the disease progresses with age to the advanced stage, it generally progresses to either the non-neovascular (“atrophic, dry”) form of AMD or the neovascular (“wet or exudative”) form of the disease (Mitchell et. al., 2018). In the dry, atrophic form, loss of photoreceptors, RPE cells and associated capillaries (choriocapillaris) in the macula result in marked thinning and/or atrophy of retinal tissue. This collective phenotype in the advanced stage of dry AMD is termed geographic atrophy (GA) (Holz et al, 2014). Furthermore, development or progression of geographic atrophy over time is a common cause of vision loss in patients diagnosed with the wet form of advanced AMD who are treated with anti-VEGF therapy, indicating that in many patients regardless of having the dry or the wet form of AMD, the final anatomic outcome leading to loss of vision is geographic atrophy (Bhisitkul et al., 2015; Grunwald et al., 2017; Abdelfatah et al., 2016).

Geographic atrophy is a significant cause of bilateral, irreversible and severe loss of functional vision, with a potential loss on average of 22 letters over 5 years, and is associated with a major impact on functional vision, quality of life, and independence (Mitchell et al., 2018;

Sivaprasad et al., 2019; Boyer et al. 2017, AREDS Report Number 26, 2009). The median time for development of central geographic atrophy from the time of diagnosis is 2.5 years with an expectancy of development in the fellow eye in approximately 7 years (AREDS Report Number 26, 2009).

Although anti-VEGF therapy is available for treatment of wet AMD, currently no Food and Drug Administration (FDA) or European Medicines Agency (EMA) approved treatment is available for geographic atrophy (Brown et al., 2006; Rosenfeld et al, 2006; Heier et al., 2012; Martin et al., 2012; Boyer et al. 2017).

The absence of treatment options for geographic atrophy secondary to AMD represents an area of urgent unmet medical need and a major public health concern for the rapidly increasing elderly population.

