7.3 Ophthalmologic Examination

The following examinations will be performed at all time-points specified in Section 10.2 “Trial Assessments”.

- Inspection of the eyelids
- Examination of extra-ocular muscle movement
- Inspection of the cornea
- Examination of the anterior chamber for inflammation (Appendix 17.1)
- Examination of the pupils
- Examination of the iris
- Inspection of the lens
- Inspection of the vitreous body (Appendix 17.2)
- Inspection of the retina and optic disc

7.4 Fundus Photography, Fluorescein Angiography, Fundus Autofluorescence, and Optical Coherence Tomography (SD-OCT)

Color stereoscopic fundus photographs, FA, FAF, and SD-OCT will be performed at all time-points specified in Section 10.2 “Trial Assessments”.

An independent and masked Reading Center (RC) will confirm eligibility of patients prior to enrollment. All color fundus photos, FAs, FAFs, and SD-OCTs that are collected at protocol-specified time points must be sent to the RC as specified in the RC procedure manual. The RC will provide instructions for the color fundus photography, FA, FAF, and SD-OCT procedures. **During the eligibility assessment, if the FAF images were reviewed to be ungradable per the independent Reading Center, the FAF images must be repeated within 72 hours. The eligibility decision by the Reading Center is final.**

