8.2.1 Ophthalmic Inclusion Criteria

The following inclusion criteria apply to the study eye (SE), one study eye per patient. If both eyes satisfy the inclusion criteria, it is in the investigator's discretion to determine the SE.

[REDACTED]

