10.2.2 On-Trial Assessments

The following evaluations, as outlined in the Study Assessments Chart (see **Section 3**), will be performed on the days specified below.

Note:

- **Concomitant medications should be assessed at every study visit.**
- **Adverse events (AEs) and serious adverse events (SAEs) should be assessed starting at Day 1 after the first dose of study drug.**
- **Ireland, Slovakia, Poland, France, and the Czech Republic: A urine pregnancy test will be performed for any woman of childbearing potential at all monthly study visits at which a serum pregnancy test is not done.**

10.2.3 Reconfirmation of Eligibility at Day 1

- Subject will be **EXCLUDED** if any of the following criteria are met between Screening and Day 1:
 - A VA change of ≥ 5 letters
 - OR
 - Significant anatomical changes (i.e. large subretinal hemorrhage, RPE rip, pigment epithelial detachment, per Investigator discretion)
 - OR
 - If the Snellen Equivalent is no longer between 20/25 - 20/320

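### In both SAPs the study-eye macula is scored only normal/abnormal in the ophthalmic-examination shift table, so that row cannot separate a new macular finding from unchanged geographic atrophy

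*SAP*

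**What the plan says.** Ophthalmic examination is a safety endpoint in the protocol (sections 5.2 and 11.2.2) and in both SAPs. The Year 1 SAP, under Safety Evaluation, Ophthalmic Variables, tabulates a list of structures as shifts from Baseline to the pre-injection examination at Month 12 or the last visit, "whichever comes later (normal/abnormal, unless otherwise specified below". One item is "Inspection of the macula", with nothing further specified. Year 2 SAP section 4.3.5 repeats the item and the default scale, with Month 24 as the end point.

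The protocol synopsis defines the population as "Patients of either gender aged 50 years or greater diagnosed with geographic atrophy secondary to AMD". Section 8.2.1 states: "The following inclusion criteria apply to the study eye (SE), one study eye per patient". The ophthalmic criteria themselves are blacked out. Section 7.4 adds: "An independent and masked Reading Center (RC) will confirm eligibility of patients prior to enrollment". Section 4.1 describes the disease as cell and capillary losses that "in the macula result in marked thinning and/or atrophy of retinal tissue". The Year 1 SAP's list of Baseline imaging variables also refers to the lesion as macular GA.

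**The concern.** A normal/abnormal shift table registers worsening only in eyes that start normal. Here the structure in question is the one that defines the disease, and it is expected to be abnormal in every study eye from the start. The macula is therefore the one structure in the list for which the binary scale cannot do its job in the treated eye.

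The macula is also where a safety signal would be looked for. Protocol section 4.3.4 reports study-eye CNV over 12 months in the earlier trial in 6 patients (9.0%) on Zimura 2 mg and 3 patients (2.7%) on Sham. A systematic examination summary is useful because it does not depend on someone deciding that a finding is an adverse event. For the study-eye macula, this row does not provide that.

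**Working it through.** The documents give no figure to reproduce. The check is the logic of the table, followed by a comparison with how the SAPs treat similar variables.

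**1. The table.** For study eyes in one arm:

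| | Normal at last visit | Abnormal at last visit |
|---|---|---|
| Normal at Baseline | a | b |
| Abnormal at Baseline | c | d |

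The only worsening cell is b, and b cannot exceed a + b, the number of eyes normal at Baseline. With about 400 patients randomized 1:1, each arm has about 400 / 2 = 200 study eyes. If a proportion p is rated normal at Baseline, b is at most 200 × p.

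The documents do not give p. The GA diagnosis points to p = 0, and then b = 0 in both arms. As an assumed range for inconsistent rating:
- p = 0.02 gives b of at most 200 × 0.02 = 4 eyes per arm.
- p = 0.05 gives b of at most 200 × 0.05 = 10 eyes per arm.

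Such shifts would come from eyes with GA that had been rated normal, so they would largely reflect inconsistent rating.

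**2. Where a new finding goes.** An eye with GA that develops CNV or a haemorrhage is abnormal before and after, so it falls in d. An eye with unchanged GA also falls in d. The remaining cell, c, is abnormal to normal, which is not a new finding.

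**3. Illustration.** Assume the earlier trial's CNV rates in 200 study eyes per arm: 200 × 0.090 = 18 eyes on Zimura and 200 × 0.027 = 5.4 on Sham. With p = 0, none of these would appear as a shift in this row. The rates rest on 6 and 3 patients, so this is not a forecast.

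**4. Contrast within the SAPs.** In the same section, anterior chamber cells and vitreous haze have graded scales, and lens status has grades plus a listing of changes. The peripheral retina is tabulated monthly, the macula only at the end. For laboratory values, both SAPs add Baseline-relative criteria for patients already abnormal at Baseline. No such rule is given for the macula.

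**5. Other outputs that could show a new macular finding.** Both SAPs tabulate ocular treatment-emergent adverse events by preferred term and by eye, and study-eye serious ocular events. The Year 1 SAP (General Conventions) promises individual listings of all CRF and external data, including CRF items that appear in no table. The visible Year 2 text has no matching sentence, although its addendum (section 5.2) says the data will be analysed in a similar way to Year 1. Protocol section 10.3 requires suspected study-eye CNV to be imaged and confirmed by the reading center before anti-VEGF treatment.

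**The case against.** The strongest reply is that this is one descriptive row and macular safety is reported elsewhere. Observed adverse events must be recorded (Protocol section 12.2), and their incidence by preferred term, arm and eye is close to what one would want. In Year 1, recorded findings are also listed patient by patient. This stands, and it rules out a stronger claim that a reader might infer: that new macular findings would be seen only if reported as adverse events. It does not make the row informative. Under Protocol section 12.1 an objective finding becomes an adverse event through symptoms, intervention, a treatment change, a serious outcome or judgment, and lack of efficacy is not recorded as one. A silent finding in an eye with progressive disease could be put down to the disease. Listings do not compare arms.

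A second reply is that normal and abnormal are not defined for the macula and the ophthalmic criteria are redacted. That also stands. A reader might infer that exactly 100% of study eyes are abnormal and that sensitivity is exactly 0%. The documents support an expectation, not a measured figure, and it applies to this row, not to the whole endpoint.

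A third reply is that blacked-out SAP sections may contain a CNV or macular summary. This is correct, so nothing here asserts that none exists.

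Finally, an empty normal-at-Baseline row would probably be recognised as uninformative. That it would be taken as reassurance is possible but speculative.

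**Conclusion.** The point holds for the study-eye macula row in both SAPs. On the expectation that study eyes with confirmed GA are rated abnormal at Baseline, the row shows no worsening in either arm, at Month 12 or Month 24, whatever occurs. If a few were rated normal, the bound in the working applies and the shifts would be hard to interpret.

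The consequence is small: a part of a stated safety endpoint that carries no information on new findings in the treated macula. No hypothesis test, error rate or primary analysis depends on it. Fellow eyes without macular disease could still shift, but they do not receive study treatment. The documents do not support saying that macular safety goes unreported in this trial. This is an inexpensive improvement, not a flaw that threatens the conclusions.

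**What to change.** For the study eye, replace or supplement the macula row in both SAPs with the number and percentage of eyes, by arm, that have a new or worsened macular finding since Baseline. Give it by type, as recorded at the masked pre-injection examination, up to Month 12 in the Year 1 SAP and Month 24 in the Year 2 SAP. Show reading-center-confirmed CNV as a separate line. Keep normal/abnormal for the other structures and for the fellow eye.

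Two limits keep this practical. First, use only data already recorded. Angiography is scheduled only at Screening, Month 12 and Month 24 (Protocol section 3), and the visible text does not show that the reading center grades every type of finding at each visit, so the table should not require new image grading. Second, do not import the Day 1 rule in Protocol section 10.2.3, "Significant anatomical changes (i.e. large subretinal hemorrhage, RPE rip, pigment epithelial detachment, per Investigator discretion", as the on-study definition. It is an exclusion rule for the interval between Screening and Day 1, and it leaves out CNV.

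The cost is one table per SAP and some masked coding of recorded findings before database lock. It assumes that the CRF holds a description of the abnormality as well as the normal/abnormal rating. No CRF is among the documents, so that should be confirmed first.
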